Participants will be randomized to one of the three groups (Massage, Joint Mobilizations, or Control) in a 1:1:1 ratio using sealed envelopes generated by the biostatistician. More specifically, we will be using a block randomization technique at each institution so that preliminary data analysis, data monitoring, and safety evaluations will be based on similar, if not identical, numbers in each group. Each block of envelopes will be made and sealed before study enrollment begins and randomization will occur after the baseline evaluation (see section 9.b of Appendix 1). The biostatistician will generate the master randomization list and distribute the envelopes. Each participant will select a sealed envelope containing their group assignment. This assignment will be noted by the research team and recorded.

SECTION I: Blinding / Unblinding

SECTION I: Blinding / Unblinding

SECTION I: Blinding / Unblinding

As per section 11 of Appendix 1 blinding will be used in the current investigation. Due to the nature of the intervention, participants will not be blinded but the assessors of the outcome measures will be blinded to group assignment.

SECTION J: Study Intervention

SECTION J: Study Intervention

The treatments as outlined in section 9.c of Appendix 1 will include:

Sensory-Targeted Rehabilitation Strategies. This intervention will consist of 6, 5-minute treatments the following over a 2-week period:

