Interested participants will be asked to fill out on-line questionnaires regarding their age, history of ankle injury (All), ankle function (FAAM, FAAM-S), and any balance issues to determine eligibility for participation in the study (Appendix 2-4). To be eligible, individuals must meet the following criteria as outlined in section 7 of Appendix 1 and section F.4 of the MOOP. In addition, participants will complete three 1-item questionnaires related to their expectations of treatment efficacy (Appendix 5). These responses will be used to match participants based on their expectations of the treatments to be provided.

Males and females between the ages of 18 and 45 with self-reported CAI; defined as self-reported episodes of recurrent ankle sprains and/or the feeling of instability or “giving way” after an initial ankle sprain. Inclusion criteria will consist of a history of at least two episodes of “giving way” within the past 6 months; answering 5 or more questions of “Yes” on the Ankle Instability Instrument (All); a score of < 90% on the self-reported Foot and Ankle Ability Measure (FAAM); a score of < 80% on the FAAM Sport. Exclusion criteria will consist of reporting an acute ankle sprain within the past 6 weeks; a previous history of ankle surgeries; lower extremity surgeries associated with internal derangements, reconstructions, or repairs; lower extremity injuries within the past 6 months (other than ankle sprains); and balance deficits, neuropathies or other disorders or conditions known to affect balance.

**If a participant is determined to be ineligible for the investigation, then the data collected (to determine eligibility) will be immediately destroyed. Specifically, the All, balance questionnaire, FAAM, and FAAM-S, data sheets must be shredded immediately. No other data can be collected prior to the participant reading and signing the informed consent document.

K.2.b Visit 1:

Informed Consent Process

Once eligible, participants will be schedule to report to the research laboratory of the PI at their respective institution. Once there, eligible participants will first read and sign the informed consent document as outlined in section H. Information will then be collected regarding height, leg length, foot measurements, and weight (see Appendix 17) as well as physical activity and overall function (see Appendix 3 & 4). Height, leg length, and

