All participants will also be asked to stand barefoot on one leg with eyes closed and hands on hips on the floor for 20 seconds to quantify their balance. Each participant will perform up to 5 trials on each leg. During each trial, the investigator will count the amount of balance errors the participant commits. Errors include any of the following: (1) lifting the hands off the iliac crests; (2) opening the eyes; (3) stepping, stumbling, or falling; (4) moving the hip into more than 30 degrees of flexion or abduction; (5) lifting the forefoot or heel; or (6) remaining out of the test position for longer than 5 seconds. The *Weight Bearing Lunge Measure (WBLT)* is a method of measuring dorsiflexion range of motion and is completed barefoot by placing the participant's great toe in line with their heel on top of a tape measure on the floor. While keeping the heel firmly on the ground, participants are asked to bend their supporting knee to touch the wall in front of them. This is completed through a slow and controlled lunging action. Using the tape measure on the floor, the maximum distance each participant can place their foot away from the wall while keeping both the heel flat on the floor and knee touching the wall will be recorded. This test will be repeated 6 times during each laboratory session. All tertiary measure methodology is consistent with those previously used by our research team.

Randomization

As per section 8 of Appendix 1 and H of the MOOP, participants will be randomized to one of the three conditions in a 1:1:1 ratio using sealed envelopes after being stratified based on treatment expectations (Appendix 5). More specifically, we will be using a block randomization technique so that preliminary data analysis, data monitoring, and safety evaluations will be based on similar, if not identical, numbers in each group. Each block of envelopes will be made and sealed before study enrollment begins by the biostatistician and randomization will occur after the baseline evaluation (see section 9.b of Appendix 1 or K.1.a of the MOOP). Each participant will select a sealed envelope containing their group assignment. This assignment will be noted by the respective PI and recorded.

First Treatment Session

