Participants will be randomized to one of groups in a 1:1:1 ratio after stratification based on treatment expectation responses. This process will happen using sealed envelopes prepared by the study biostatistician. More specifically, we will be using a block randomization technique at each institution so that preliminary data analysis, data monitoring, and safety evaluations will be based on similar, if not identical, numbers in each group. Each block of envelopes will be made and sealed before study enrollment begins and randomization will occur after the baseline evaluation (see section 9.b below). The biostatistician will be responsible for generating the master randomization list and each participant will select a sealed envelope containing their group assignment. This assignment will be noted by the PI and recorded. Assessors will be blinded to group assignment.

9 Screening Process, Baseline Evaluation, Study Treatment, & Final Evaluation

9.a Screening Process

The screening process will be performed at a specific eligibility screening session. At this session, potential participants will complete the Balance Questionnaire (Appendix 2), All (Appendix 3), FAAM (Appendix 4), FAAM-Sport (Appendix 4), and Treatment Expectation (Appendix 5) questionnaires. If eligible, participants will be scheduled for baseline testing which will be the first of 3 testing sessions. The first will take place on the day of baseline evaluation. The second will take place at the end of the 2-week intervention. The third will take place 1-month after the final treatment session.

9.b Baseline & Post-Test Evaluations

The baseline evaluation will include gathering general information regarding age, height, leg length, foot measurements, weight. Participants will then receive instruction on the testing procedures and will perform several warm-up trials on all assessments to become familiarized with the testing procedures. Next, participants will have their ankle range of motion, postural control, and lower extremity biomechanics tested. Finally, participants will complete the possible neuromuscular mechanism measures. All outcomes will be performed at all test sessions. More detailed descriptions are provided below:

[figure not shown]
Peripheral Neuromuscular Mechanisms:

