Appendix 5: Treatment Expectations Questions

Manual therapies will improve my CAI related impairments?

1 2 3 4 5
No Confidence Neutral Very Confident

Ankle joint mobilizations will improve my CAI related impairments?

1 2 3 4 5
No Confidence Neutral Very Confident

Plantar massage will improve my CAI related impairments?

1 2 3 4 5
No Confidence Neutral Very Confident

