Intervention Delivery: After completion of baseline testing, participants will be randomized into 3 groups to receive interventions identical to our previous work.^{42, 71} All interventions are to a single limb and require 6, 5-minute treatment sessions over 2-weeks. The first group (n=20) will receive 2, 2-minute bouts of Grade III anterior-to-posterior talocrural joint mobilization with 1-minute between sets during each session. Mobilizations will be large-amplitude, 1-5 rhythmic oscillations from the mid- to end range of arthrokinematic motion. The second group (n=20) will receive 2, 2-minute plantar massage bouts with 1-minute between sets during each session. The massage will be a combination of petrissage and effleurage to the entire plantar surface. The third group (n=20), a control condition, will receive no treatment during the entire 2-week intervention period. All groups will be instructed to continue regular physical activity habits and daily routines over the course of 2-week intervention.

A.4.3. If subjects are assigned or randomized to study "arms" or groups, describe how they are assigned.

- Describe the methods of computing the randomization schedule (if any) and maintaining blinding (if any).
- Who will perform these computations?
- How will you verify each subject's eligibility prior to randomization?

Participants will be randomized and allocated in a 1:1:1 ratio within blocks (n=6) using sealed envelopes generated by the study biostatistician.

IRB Number: 17-2655	Initial	Principal Investigator: [name]
---------------------	---------	---------------------------------------

Eligibility will be determined by questionnaire, consistent with best practices research within the field of chronic ankle instability.

A.4.4. Describe any follow up procedures.

A 4-week follow up after the intervention will be conducted. This assessment is identical to those conducted immediately before and after the intervention and is described above in A.4.2.

A.4.5. Once this study has been approved by the IRB, for how many months or years will this study be active (you are collecting data or have access to identifiers)?

36-months.

A.4.6. Will this study use any of the following methods?

 Audio Recording
 Video Recording

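### Sections disagree on whether randomisation is stratified by treatment expectation, the strata are not defined, and the primary model has no stratum term

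*Combined protocol and SAP*

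**What the plan says.** The allocation is described in five places.

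- **Appendix 1, Section 8:** allocation "in a 1:1:1 ratio after stratification based on treatment expectation responses". The envelopes come in blocks that are made and sealed before enrolment opens.
- **MOOP K.2.b (Randomization):** also stratifies on the Appendix 5 expectations, and cites both Section 8 and Section H as its source.
- **MOOP K.2.a:** "These responses will be used to match participants based on their expectations of the treatments to be provided".
- **MOOP Section H:** allocation "in a 1:1:1 ratio using sealed envelopes generated by the biostatistician". It mentions blocks but gives no stratum and no block size.
- **Appendix 18, A.4.3:** allocation "in a 1:1:1 ratio within blocks (n=6) using sealed envelopes generated by the study biostatistician". It names no stratum, and it is the only place with a block size.

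Appendix 5 has three items, each scored 1 to 5: one on manual therapies in general, one on joint mobilisation, and one that reads "Plantar massage will improve my CAI related impairments". Nothing says whether they are used singly, summed, cut or crossed. Sections H and 8 also speak of blocking at each institution, although Section 5 gives one site.

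Section 12 of Appendix 1 and A.8.1 of Appendix 18 specify a Group × Time ANOVA with no term for expectation. The sample size text (M.5 and Section 6) asks for 18 per group and recruits 20 to allow for 10% dropout.

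**The concern.** Participants know their treatment and the control group receives none, so expectation could plausibly affect the result, and balancing it is a sensible aim. The text does not let anyone carry that aim out. A biostatistician preparing stratified envelopes needs the stratum variable, its cut-points and the block size in advance. Each participant is to pick an envelope, but the text does not say from which set.

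The choice also matters statistically. Permuted blocks hold arm sizes together only where blocks fill. With 60 participants and many small strata most blocks stay incomplete, and the blocking loses most of its purpose. The margin is two participants per arm (20 recruited, 18 needed). Finally, a factor that governs allocation would normally appear in the primary model, and here it does not.

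**Working it through.** **The plan's own figures.** The dropout step reproduces: 18 / 0.90 = 20 per group, 60 in total. The 18 does not reproduce from the stated model (repeated measures, between factors, 3 groups, m = 2 time points, ρ = 0.90). With λ = f²·N·m / (1 + (m − 1)ρ) and f = d/2, 90% power needs 59 per group for d = 0.53 and 35 for d = 0.69. That is a separate matter. The power figures below take 18 per group = 90% as given.

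**Inputs.** N = 60 and 1:1:1 (Sections 6 and 8), blocks of 6 (A.4.3), three items with five levels (Appendix 5), 10% dropout (Section 6). Response distributions are not in the documents and are assumed:

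- uniform;
- concentrated, with probabilities 0.03, 0.07, 0.35, 0.35, 0.20 for scores 1 to 5;
- concentrated and correlated, where each of the other two items copies the first with probability 0.6.

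**Cells.** Full crossing gives 5 × 5 × 5 = 125. One block of 6 for each cell would take 125 × 6 = 750 envelopes.

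**Power.** For arms of size a and b, power = Φ(δ·√(1/(1/a + 1/b)) − 1.96). Here δ is set so that 18 v 18 gives 90%: δ = (1.960 + 1.282)·√(2/18) = 1.08. Then 20 v 20 gives 92.7%, 16 v 24 gives 91.7% and 14 v 20 gives 87.3%. For dropout, both arm sizes are multiplied by 0.9.

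**Simulation** (20,000 trials per row). Range is largest minus smallest arm. The single-item row uses the concentrated distribution; the other coarse rows use the correlated one.

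| Strata | Cells occupied | Exactly 20/20/20 | Median range | Smallest arm <18 | Mean power after dropout | 5th percentile |
|---|---|---|---|---|---|---|
| None | 1 | 100% | 0 | 0% | 90.0% | 90.0% |
| Two levels | 2.0 | 38.7% | 2 | 0% | 90.0% | 89.2% |
| One 5-point item | 4.8 | 14.0% | 2 | 3.5% | 89.9% | 88.4% |
| Three items, each cut in two | 7.4 | 9.4% | 3 | 10.7% | 89.8% | 88.1% |
| Sum score, 13 levels | 10.3 | 6.8% | 3 | 18.8% | 89.8% | 87.6% |
| 125 cells, correlated | 23.1 | 3.1% | 5 | 45.9% | 89.5% | 85.8% |
| 125 cells, concentrated | 34.6 | 1.9% | 6 | 59.8% | 89.2% | 84.5% |
| 125 cells, uniform | 47.8 | 1.4% | 7 | 66.5% | 89.0% | 83.6% |
| Simple randomisation | – | 1.3% | 7 | 69.0% | 88.9% | 83.1% |

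Before dropout, mean power under full crossing is 91.8% to 92.3%, against 92.7% with no strata. The average loss is therefore 0.4 to 0.9 points before dropout and 0.5 to 1.0 after. At the 5th percentile after dropout the loss is 90.0 − 85.8 = 4.2 to 90.0 − 83.6 = 6.4 points.

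**Why two strata are safe.** Each stratum leaves at most 5 people in an incomplete block. The two remainders must sum to a multiple of 6, so to 0 or 6. At least 54 people are then in complete blocks, and every arm has at least 54 / 3 = 18.

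**Balance on expectation.** Full crossing puts 60 / 47.8 = 1.3 to 60 / 23.1 = 2.6 people in each occupied cell, too few for blocks of 6 to balance much within a cell.

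**The case against.** The strongest reply is that there is one scheme, unevenly described. K.2.b cites Section H and Section 8 together and then stratifies, so the authors evidently regard them as the same plan, with the factor left out of Section H. Neither Section H nor A.4.3 says that allocation is unstratified; that is inferred from silence. No matched-set procedure appears anywhere, so the word match in K.2.a is most naturally a loose term for balancing on the same responses. The IRB application is dated October 2017 and the MOOP questionnaires December 2017, so A.4.3 may simply be older. All of this is fair. A reader might infer three rival designs, and the documents do not go that far.

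The reply is also right that nothing says the three items are crossed. The ordinary choices (one item, a cut score, three dichotomised items) cost 0.2 points of average power or less. The plan itself asks only for near-equal group numbers, and it cites 98.75% retention in earlier work.

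What remains is that the most charitable reading, stratified blocks, still lacks the item, the cut-points and the number of strata, and takes its block size from a section that names no stratum. The envelopes cannot be prepared from this text.

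**Conclusion.** The point holds as an inconsistency with a cheap remedy. The five descriptions need to be reconciled, the expectation strata need defining before envelopes are sealed, and the primary model should carry the stratum.

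The size depends on a choice that the documents leave open. With few strata the effect on arm sizes and power is negligible. With the finest possible split, blocking would work little better than simple randomisation, with some arm starting below 18 in about 46% to 67% of trials. These figures rest on assumed response distributions, on blocks of 6, and on 18 per group giving 90%.

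Two stronger readings are not supported:

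- **That stratifying would destroy a 1:1:1 balance the sample size needs.** Full crossing is only an assumption. Even under it the expected allocation stays 1:1:1, the total stays 60 and average power moves by a point or less. The 18 used as the benchmark does not itself follow from the stated model.
- **That the analysis is undefined until the scheme is settled.** The Group × Time ANOVA can be run under any of these schemes. Leaving out the stratum is a weakness, but it does not prevent the analysis.

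**What to change.** Use one description in Section H, K.2.a, K.2.b, Appendix 1 Section 8 and A.4.3: permuted blocks within a small number of expectation strata. Two would do, from one pre-set cut of an item or summary score. The sponsor should choose which, since K.2.a speaks of expectations of the treatments provided and a general item may not capture that. State the item or score, the cut-point, the block size and that envelopes are kept by stratum. Replace the matching wording in K.2.a and remove the reference to blocking at each institution.

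Add the stratum to the primary model in Section 12 and A.8.1. Because the test of interest is Group × Time, the stratum should enter together with its interaction with time; a main effect alone would not adjust the comparison of changes.

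The cost is wording in these seven places, a regenerated list, and one model degree of freedom per extra stratum in the two-time-point comparison (with 54 evaluable, 54 − 3 = 51 error degrees of freedom become 50 for two strata). Expectation items not used for the strata would no longer be balanced by design, though they can still be reported by arm.

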Neuromuscular mechanisms will be quantified before and immediately after a 2-week intervention. Mechanisms will include a comprehensive group of peripheral (ankle joint position sense, plantar light-touch discrimination thresholds), spinal (H-reflex of the soleus and fibularis longus), and supraspinal measures (cortical activity during stance using electroencephalography [EEG], corticomotor excitability and mapping of the soleus and fibularis longus via transcranial magnetic stimulation [TMS], and sensory organization strategies during stance). Our primary mechanism of interest is sensory organization strategies. Sixty CAI patients will be randomized into three equal groups (ankle joint mobilization, plantar massage, control) to complete 6 treatment sessions over 2-weeks.

Hypothesis 1. Both interventions, relative to the control group, will result in significant sensory organization strategy changes, representing a reduction in the CAI patient's reliance on visual information during stance.

Hypothesis 2. Each intervention will result in unique combinations of peripheral, spinal, and supraspinal mechanistic pathways relative to the control group.

Aim 2: Determine the associations among peripheral, spinal, and supraspinal neuromuscular mechanisms, secondary biomechanical measures, and sensory organization strategies in CAI patients. These associations will be quantified to elucidate the unique combination of peripheral, spinal, and supraspinal mechanistic pathways thought to contribute to a reducing in the reliance of visual information during stance. Secondary measures which will include jump landing and gait biomechanics will be assessed before and immediately after the 2-week interventions. We will use an analytical approach (see statistical analysis) to determine simple associations at baseline, post-test, and among change scores in neuromuscular mechanisms and secondary measures.

Hypothesis 1. Each intervention will result in unique combinations of changes in peripheral, spinal, and supraspinal mechanistic pathways will be strongly associated with changes sensory organization strategies.

Hypothesis 2. Each intervention will result in secondary measure changes associating with changes in sensory organization strategies as well as peripheral, spinal, and supraspinal mechanistic pathways.

3 Study Design

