will assess spinal reflexive excitability in the soleus and fibularis longus using our established methodology. While lying supine, a stimulating electrode will be positioned over the sciatic nerve in the popliteal space. Peak-to-peak Hoffmann reflexes (H-reflex) will be measured and the stimulus intensity increased until a maximal H-reflex is observed. Three H-reflexes for each muscle will be recorded and normalized to the maximal M-response, representing the ratio of the motor neuron pool reflexively activated to the amount of the motor neuron pool available (H:M ratio). Higher H-reflex values and H:M ratios indicate greater excitability.

Supraspinal Level Mechanisms:

The corticospinal motor system plays a critical role in controlling movement by optimizing muscle activation. Abnormal facilitation or inhibition from the corticospinal pathway is associated with impairments of the ankle joint musculature and hypothesized to contribute to the postural instability associated with CAI. As such, cortical excitability may represent a plausible neuromuscular mechanism underlying improvements following ankle joint mobilization and plantar massage. Corticomotor measures of the soleus and fibularis longus will be assessed using Transcranial Magnetic Stimulation (TMS) methodology previously used by the research team. A Magstim 200 (Magstim Company, Wales, UK) will be used to produce a magnetic stimulus (max 2.0 Tesla) over the motor cortex contralateral to the test limb. Testing will be performed over the area generating the greatest motor evoked potential (MEP) while participants perform mild isometric contractions (20%) on an isokinetic dynamometer. Active motor threshold (AMT) will be determined as the lowest stimulator intensity required to elicit an MEP peak-to-peak amplitude $\geq 100\mu\text{V}$ in at least 4 of 8 trials. A higher AMT indicates decreased excitability, as a greater stimulus intensity is required to elicit an MEP. Eight stimuli will be delivered at 120%, 130%, and 140% of AMT, and peak-to-peak MEP amplitudes will be recorded for each trial. The cortical silent period (CSP) will be measured as the distance from the end of the MEP to a return of the mean EMG signal plus two times the standard deviation of the baseline (pre-stimulus) EMG signal. A longer CSP indicates a greater corticospinal inhibition.

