Corticomotor output mapping provides further insight into the function of the motor cortex by identifying the size of an area within the motor cortex associated with a select muscle. Improved postural control following manual therapies may be the result of a reorganization of the corticomotor output in CAI patients (i.e. an increased map area and/or volume of a given muscle). Corticomotor mapping of the soleus and fibularis longus muscle will be assessed using TMS methods consistent the literature and our own protocols. After AMT is quantified, a 6x6 cm grid (3cm lateral-medial and 3cm anterior-posterior) will outline the hotspot for each muscle and a stimulator intensity of 100% AMT will be used. Three consecutive stimuli will be delivered at each grid location in a random order in order to produce reliable and reproducible maps. Average peak-to-peak MEP amplitudes for each grid site will be normalized to M-max. Cortical representation of the soleus and fibularis longus will be calculated using map area and map volume. Map area is the number of stimulus positions whose stimulation evoked an average MEP \geq MEP threshold and an increase would suggest an expansion of the

cortical representation of a selected muscle. Map volume will be calculated as the sum of the mean normalized MEPs recorded with an increase suggesting greater cortical excitability.

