To achieve Aim 2 and determine the associations among sensory organization strategies, neuromuscular mechanisms, and secondary measures following ankle joint mobilization and plantar massage interventions, we will calculate associations at baseline, at the post-test, and among change scores. These associations will be calculated using Pearson Correlation Coefficients that will be interpreted as: ≤ 0.29 as negligible, 0.30-0.49 as low, 0.50-0.69 as moderate, 0.70-0.89 as high, and ≥ 0.9 as a very high correlation.¹³⁵ The models will then be adjusted for identified covariates using a general linear model and an exploratory alpha level of 0.10. We anticipate associations that will provide insights about how to specifically leverage the manual therapies mechanisms to target specific neuromuscular impairments and biomechanical deficits associated with CAI.

All experimental conditions are detailed to ensure reproducibility and the proposed analytic plan ensures unbiased treatment and interpretation of the data. We are committed to full transparency in reporting the results and to making the data available upon request for unbiased review.

To explore how individual response variability influences plausible neuromuscular mechanisms, we will use a Bayesian statistical approach.^{71, 94, 144, 145} More specifically, we will determine how patient characteristics (e.g. age, height) and baseline measures influence the probability of having a meaningful change in % Modulation and other neuromuscular mechanisms. Predicting treatment response with only demographic and baseline data would suggest that the neuromuscular mechanism(s) of ankle joint mobilization and plantar massage may be modulated by the patient's sensorimotor constraints.

13 Data Management

Data will be collected both in hard copy & electronically. All computers in the research laboratories are password protected. As soon as feasible, the PIs will transfer the, already de-identified, electronic data to Sharepoint. In order to protect the integrity of the original data files, copies will be made to be used for data manipulation. Any data file that is amended, cleaned, or updated will be given a new name with the corresponding name of the original file followed by `_modified` and dated with the `month_`, `day_`, and 2-digit year it was modified (i.e. `IC01_trial_1_modified_10_11_18`).

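### Within a muscle, the Aim 2 correlation of H:M ratio with TMS map volume may be inflated, because both are divided by M-max and no allowance for M-max is planned

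*Combined protocol and SAP*

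**What the plan says.** Appendix 1, section 9.b defines the spinal measure: "Three H-reflexes for each muscle will be recorded and normalized to the maximal M-response". For TMS mapping of the same two muscles it states: "Average peak-to-peak MEP amplitudes for each grid site will be normalized to M-max". It then states: "Map volume will be calculated as the sum of the mean normalized MEPs recorded with an increase suggesting greater cortical excitability". The same definitions are repeated in MOOP section K.2.b and in the IRB application (Appendix 18, A.4.2).

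Aim 2 (Appendix 1, section 2) is to "Determine the associations among peripheral, spinal, and supraspinal neuromuscular mechanisms, secondary biomechanical measures, and sensory organization strategies in CAI patients". Section 12 gives the statistic: "These associations will be calculated using Pearson Correlation Coefficients". It applies this at baseline, at post-test and to change scores. The models are then adjusted, in a general linear model at an exploratory alpha of 0.10, for covariates still to be identified. M-max is not named among them, and no analysis of unnormalized amplitudes is planned.

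The other TMS measures are defined differently. "Map area is the number of stimulus positions whose stimulation evoked an average MEP" reaches a threshold, so map area is a count of sites. For stimuli at 120–140% of AMT the plan says only "and peak-to-peak MEP amplitudes will be recorded for each trial", with no normalization stated.

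**The concern.** M-max is a single value for a muscle in a session, so map volume equals the summed MEP amplitude divided by M-max, and the H:M ratio equals H divided by M-max. If both use the same or a closely related M-max, any variation in it moves the two ratios in the same direction. A positive Pearson r can then appear when reflex and cortical amplitudes are unrelated. For change scores, session-to-session error in M-max has the same effect.

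At stake is the interpretation of one part of Aim 2. A positive H:M ratio–map volume correlation could be taken as evidence that spinal and supraspinal pathways are linked when part or all of it comes from the denominator. Dividing by M-max is a reasonable choice for the group comparison in Aim 1, and that comparison is not in question.

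**Working it through.** **Inputs.** From the documents: the two definitions, Pearson r, the three analyses (baseline, post-test, change), 18 evaluable participants per group (54 in all), and alpha 0.10 for the adjusted models. The documents give no CVs for H, MEP or M-max, so every CV below is an assumption shown over a range. The plan has no figure of its own for this pair to reproduce.

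**1. Between subjects, amplitudes unrelated to M-max.** The first-order formula is r = CVm² / √[(CVh² + CVm²)(CVv² + CVm²)], where m is M-max, h is H and v is summed MEP. With CVm = 0.3 and CVh = CVv = 0.5, r = 0.09 / (0.25 + 0.09) = 0.26. Lognormal simulation gives 0.25. With CVh 0.25–0.40 and CVv 0.25–0.60:

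| M-max CV | induced r |
|---|---|
| 15% | 0.08–0.26 |
| 25% | 0.19–0.49 |
| 40% | 0.36–0.69 |

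**2. Between subjects, both amplitudes scale with M-max.** Suppose a common recording gain multiplies H, MEP and M-max (gain CV 0.3 or 0.5, amplitude CV 0.5). Raw amplitudes then correlate 0.25 or 0.45 with no true association, and an error-free M-max brings the ratio correlation to 0.00. With M-max error CV of 5%, 10% and 20%, the ratio correlation is about 0.01, 0.04 and 0.13.

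**3. Change scores, full scaling.** A stable gain cancels between sessions, but M-max error does not. For log changes, r = s_e² / (s_n² + s_e²), where s² = ln(1 + CV²), e is M-max session error and n is session noise in each amplitude. With error CV 10% and noise CV 20%, r = 0.00995 / (0.03922 + 0.00995) = 0.20. For plain differences of the ratios, simulation with noise CV 20% gives about 0.05, 0.16, 0.30 and 0.41 at error CV 5%, 10%, 15% and 20%. At 20% the value runs from 0.39 to 0.45 depending on the between-subject spread of H and MEP.

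**4. Effect on tests (two-sided, nominal 10%).** An induced r of 0.16 is significant in 17% of analyses at n = 18 and 32% at n = 54. An induced r of 0.25 is significant in 27% and 58%.

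**5. Does the partial correlation cure it?** Because log(H/M) = log H − log M, conditioning on log M gives the same partial correlation for ratios and for raw amplitudes.
- Amplitudes unrelated to M-max (numerator CV 0.5; M-max CV 0.2, 0.3, 0.5; n = 18): the plain test rejects 16.5%, 28.8% and 60.5% of the time. The partial test rejects 9.8–10.1%, with median r 0.00.
- Change scores as in step 3: the partial r is 0.00 throughout.
- Common gain (step 2, gain CV 0.3, M-max error CV 0.2): the variance of log gain left after conditioning is 0.0862 × 0.0392 / (0.0862 + 0.0392) = 0.0270. The partial r is 0.0270 / (0.2231 + 0.0270) = 0.11, against 0.0392 / (0.2231 + 0.0392) = 0.15 for the log ratios. It is smaller, but not zero.

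**The case against.** The strongest reply is that normalization exists to remove an artefact. The plan describes H:M as a share of the available motor neuron pool, which implies that H scales with M-max. If MEPs scale too, dividing by M-max removes a spurious raw correlation of 0.25–0.45 and leaves little (step 2). If only H scales, the induced r is 0.00 without M-max error and 0.09–0.11 with error CV 20%. This stands for the between-subject correlations, whose inflation may be small. It does not rescue change scores, where stable gain has already cancelled and session error in M-max remains in both ratios.

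Second, the documents do not say that one M-max recording serves both measures. H-reflexes are taken supine, and TMS is done on a dynamometer under contraction. Against that, no separate M-max acquisition is described for mapping. With separate recordings, unrelated amplitudes and M-max CV 0.3, the induced r is 0.00, 0.12 or 0.22 for a log-correlation between recordings of 0, 0.5 or 0.9. So the artefact is possible but not established.

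Third, a reader might infer that the spinal–supraspinal associations of Aim 2 in general are products of the denominator, or that the Aim 2 hypotheses are compromised. The documents do not support this. Map area is a count, AMT, CSP and EEG power are not M-max ratios, and no normalization is stated for MEPs at 120–140% of AMT. The first Aim 2 hypothesis says that mechanism changes "will be strongly associated with changes sensory organization strategies", which is % Modulation and contains no M-max. The second pairs secondary measures with % Modulation and the mechanisms. The exposed pair enters only through the general wording of the aim.

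It is also tempting to set the induced r beside the r = 0.5 used for sample size. That value comes from correlations of mechanisms with biomechanical measures of postural control, so it is not a benchmark for this pair. Section 12 also grades r up to 0.29 as negligible, so a small induced r would not be called a finding on size alone. And section 12 ties alpha 0.10 to the adjusted models without giving an alpha for the plain Pearson tests.

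**Conclusion.** The concern holds for one pair of measures, H:M ratio against map volume within the same muscle, for soleus and for fibularis longus, at baseline, at post-test and on change scores. Those correlations may be inflated by the shared denominator, and the plan makes no allowance for it.

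The induced r is about 0.01–0.13 between subjects if H and MEP scale with M-max (M-max error CV 5–20%), and about 0.08–0.69 if they are unrelated to it (M-max CV 15–40%). For change scores it is about 0.05–0.45 at session M-max error CV 5–20%, even with full scaling. The upper part of that last range falls in the band that section 12 grades as a low rather than a negligible correlation.

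All these figures rest on assumed CVs and on one M-max value entering both ratios. The case is firmest for change scores. The primary mechanism, the Aim 1 comparisons and correlations with % Modulation are untouched. This is a cheap improvement to an exploratory analysis.

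**What to change.** Add one sentence to section 12. For H:M ratio against map volume in the same muscle, the Aim 2 association is based on the partial correlation of log H amplitude and log unnormalized map volume given log M-max. For change scores, it uses log changes given the change in log M-max. Fit it in the general linear model already planned, and report the ratio correlation beside it. State whether one M-max recording serves both measures. Keep the ratios for Aim 1.

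The cost is that sentence and one degree of freedom per model. M-max is already needed to form the ratios, so no new data are required. The adjustment should be fixed before analysis, since the ratios alone cannot show how much of a correlation comes from M-max.
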